6.6. Randomisation Procedure / Code Break

N/A – open label trial – volunteers and the research team are aware of which IMP a volunteer has been allocated to.

6.7. Withdrawal of Participants

Participants have the right to withdraw from the study at any time for any reason. The investigator also has the right to withdraw participants from the study drug in the event of inter-current illness, AEs, SAEs, SUSARs, protocol violations, cure, administrative reasons or other reasons. It is understood by all concerned that an excessive rate of withdrawals can render the study un-interpretable; therefore, unnecessary withdrawal of participants should be avoided. Should a participant decide to withdraw from the study, all efforts will be made to report the reason for withdrawal as thoroughly as possible. Should a participant withdraw from study drug only, efforts will be made to continue to obtain follow-up data, with the permission of the participant.

A subject may be withdrawn in any of the following circumstances:

AE.

Protocol violation.

Withdrawal of consent.

Study drug administration may also be stopped for a subject due to a decision by the Investigator, see Section 9.4 for further details.

The Investigator should as far as possible have the subject complete the scheduled discharge assessments and also have the subject attend a follow-up visit after 1 day (± 1 day) following completion of the study. This could be modified where justified at the Investigator's discretion.

Investigators should attempt to obtain relevant information on subjects in the case of a subject withdrawal. For subjects considered as lost-to-follow-up, the Investigator should make an effort (at least one phone call and one written message to the subject), and document his/her effort (date and summary of the phone call and copy of the written message in the source documents), to complete the final evaluation. All results of these evaluations and observations, together with a narrative description of the reason(s) for removing the subject, must be recorded in the source documents. The case report form (CRF) must document the primary reason for withdrawal or discontinuation.

Subjects who voluntarily withdraw are termed dropouts. Dropouts may be replaced following discussion with the Investigator and Sponsor. Subjects withdrawn due to an AE will not be replaced.

6.8. Expected Duration of Trial

The beginning of the trial will be defined as first patient first visit and the end of trial will be defined as database lock.

Active participation in the trial for each volunteer is for 6 days and each individual participant will remain on trial until the morning of day 6 - final visit.

7. Trial Procedures

7.1. By Visit

Each participant will have pre-entry screening. For practical reasons, this may be conducted at the subject's home. Each home visit for the purposes of the trial will be conducted by a researcher and a chaperone. Following informed consent for the study has been obtained, the research team will check her medical history and physical health (including vital signs), as well as ask volunteers to have screening bloods. The procedures during each visit are detailed in Table 4-1.

7.1.1 Screening Visit

The following study evaluations will be performed/recorded during the course of the screening period (28 days):

- Signed informed consent
- Inclusion and exclusion criteria
- Record past medical and social history
- Record of concomitant medication usage, including contraindicated/restricted medication
- Participant demographics
- Pregnancy test
- Blood sampling (safety bloods)
- Vital signs

7.1.2 Day 1 (0hr)

- Record of concomitant medication usage, including contraindicated/restricted medication
- Vital signs
- IMP administration

7.1.3 Day 1 - 3hr, 12hr and 24hr visits

- Milk and blood sampling at 3hr, 12hr and 24hr
- Update of adverse events

7.1.4 Day 2

- Vital signs
- IMP administration
- Record any adverse events

7.1.5 Day 3 - 0hr, 3hr, 12hr and 24hr visits

- Vital signs
- IMP administration (0hr)
- Milk and blood sampling at 3hr, 12hr and 24hr
- Record any adverse events

7.1.6 Day 6 (study for participant ceases on morning of day 6)

- Record any adverse events
- 72 hr milk and blood sample
- Safety bloods

7.2. Laboratory Tests

According to the milk and blood collection time points and safety assessment schedule, the blood and milk volumes to be collected from any single subject are presented in Table 7-1.

Blood samples will be packed and transferred to King's College Hospital immediately after collection. Clinical samples (UEs/LFTs/FBC) will be handled by the Viapath, King's College Hospital. Pharmacokinetic blood samples will be cooled and centrifuged as soon as possible in the CI's laboratory at King's College Hospital. The separated plasma samples will be transferred to a clean tube and stored at -20°C.

Milk samples will be stored at -20°C in the CI's laboratory at King's College Hospital. Separated plasma samples and milk samples will then be transferred to ASI Bioanalytics (London, UK) within 56 days for the analysis. Detailed sample collection, handling, labelling, storage and shipment will be described in the Laboratory Manual at King's College Hospital and ASI Bioanalytics.

Table 7-1 Blood and Milk Volumes to be Collected in a single subject in EDX/RVX group over the course of the volunteers involvement in the trial

Assessment	Sample Volume (mL)	No. of Samples	Total Volume (mL)
Safety			
Clinical Chemistry	5.0	2	10.0
Haematology (PT, APTT)	3.7	2	7.4
FBC	2.0	2	4.0
Pregnancy test	3.5	1	3.5
Pharmacokinetic			
Plasma Samples	2.0	8	16.0
Milk Samples	10.0	8	80.0
Total (mL)			Blood: 41.0 Milk: 80.0

FSH: Serum Follicle-stimulating Hormone

Sample volumes are based on direct venepuncture.

Milk sample to be collected at any breast (10ml) by manual expression or breast pump.

Additional samples may be collected as required at the Investigator's discretion. However, the total volume of blood collected per subject during the study will not exceed 100 ml. Individual venepunctures for each time point will be performed. The exact date/time of the milk and blood sample collection will be recorded in the subject's CRF.

Time windows for the collection of the PK blood and milk samples are as follows:
±30 minutes for all sampling time points (with the exception of the pre-dose sample).

8. Assessment of Safety

8.1. Specification, Timing and Recording of Safety Parameters

The safety assessments will be relative to those risks identified in section 5.3.
Sample collection times are included in the schedule of visits and assessments.
AEs and SAEs will be reported from first dose until 24 hours following the final (third consecutive) dose.

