4.5. Trial Flowchart

[figure not shown]
Table 4-1: Trial procedures during the clinical trial – EDX and RVX groups

	Pre-sampling		Sampling								Post-sampling		
	Screening	Randomisation	Visit 1 (day 1)				Visit 2 (day 2)	Visit 3 (day 3)				Final Visit (day 6)	
			0 hr	3 hr	12 hr	24 hr	0 hr	0 hr	3 hr	12 hr	24 hr		
Written informed consent	X												
Patient demographics	X												
Eligibility assessment, including vital signs	X	X											
Past medication, medical and social history	X												
Bloods (UEs, LFTs, FBC, coag screen) – safety bloods	X												X
Pregnancy test	X												
Randomisation (if applicable)		X											
Bloods reviewed and volunteer given all clear to take part. Date arranged with volunteer to do the study sampling		X											
IMP dispense		X											
Vital signs and then IMP administration			X				X	X					
Milk sampling (+/- 30min)				X	X	X		X (pre-dose)	X	X	X	X	X

Pharmacokinetic blood samples				X	X	X		X (pre-dose)	X	X	X	X
Adverse events			X	X	X	X		X	X	X	X	X
End of trial for patient												X

Figure 4-1. Milk and blood collection time points – EDX and RVX groups

[figure not shown]
DAY 1

DAY 2

Second dose of EDX / RVX administered.

DAY 3

DAY 6

72 hours post day 3 dose.

5. Trial Medication

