5.2. Dosing Regimen

The study drug will be orally administered as tablet (edoxaban or rivaroxaban) formulation once a day on days 1, 2 and 3. The IMP will be administered at subject’s home under the guidance of the investigator with the date and time of administration recorded in the subject’s CRF.

Table 5-3 Dosing regimen

Study Arm	Study Drug Dose	Subjects	Duration for each subject* (Day -28 to day 6)		
Edoxaban (EDX)	60 mg (once daily)	6	Screening (day -28 to -3)	Treatment (day 1 to 3 inclusive)	Safety review (day 6) & study closure
Rivaroxaban (RVX)	20 mg (once daily)	6		Treatment (day 1 to 3 inclusive)	

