8.4. Premature Termination of the Trial

The trial may be prematurely discontinued by the Sponsor, Chief Investigator or Regulatory Authority on the basis of new safety information or for other reasons given by the Trial Steering Committee regulatory authority or ethics committee concerned.

If the trial is prematurely discontinued, active participants will be informed, and no further participant data will be collected. The Competent Authority and Research Ethics Committee will be informed within 15 days of the early termination of the trial.

For the edoxaban arm, following the recruitment and sampling of 2 patients, interim analysis will be completed. If significant transfer of edoxaban into human breastmilk is found, this arm of the study will cease (go : no-go criteria).

9. Statistics

Descriptive statistics will be used to analyse the data and describe the study population.

Classical non-compartmental pharmacokinetic analysis will be conducted on the breastmilk and plasma samples. AUC (0-24 hours (day 1 and day 3) and milk to plasma ratio will be computed for each volunteer and then for the cohort as a whole.

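### Section 8.1 closes adverse-event reporting 24 h after the third dose, 48 h before the protocol's own Day 6 safety visit, and Section 8.2 sets no end time

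*Protocol*

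**What the plan says.** - **Reporting window.** Protocol Section 8.1: "AEs and SAEs will be reported from first dose until 24 hours following the final (third consecutive) dose".
- **Dosing.** Section 5.2 has the tablet given as a "formulation once a day on days 1, 2 and 3".
- **Final visit.** Figure 4-1 (Section 4.5) places Day 6 at "72 hours post day 3 dose". Section 7.1.6 lists for that visit "Record any adverse events" and "Safety bloods". Table 4-1 marks both at the final visit, and Table 5-3 labels Day 6 as the safety review. Section 6.8 says that "each individual participant will remain on trial until the morning of day 6 - final visit".
- **Expedited reporting.** Section 8.2 requires SAEs, SARs and SUSARs to go to the clinical trials office immediately, and within 24 h at the latest. It excepts those that the protocol specifies as exempt. That sentence sets no last day.
- **Exemption.** Section 8.3 removes from reporting any event consistent in nature and severity with section 4.8 of the relevant SmPC, whatever its timing.
- **Laboratory data.** Under Section 16, safety results stay in the hospital system. The paper CRF and the eCRF receive only the date and time of sampling.
- **Early termination.** Section 8.4 says that if the trial is stopped, "active participants will be informed, and no further participant data will be collected".

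**The concern.** The protocol treats Day 6 as the point at which each woman's safety is assessed, yet the sentence that defines what is reported stops on Day 4. Section 5.3 names bleeding, including postpartum haemorrhage, as a main risk. Section 11 says there will be no data monitoring or steering committee, so routine event reporting is the main formal route by which a safety signal would leave the study team.

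Two people applying the protocol in good faith could treat the same Day 5 event differently, one reporting it under 8.2 and the other declining under 8.1. A reporting rule should not allow both. A statistical analysis plan would not settle this either, because the reporting period for adverse events belongs in the protocol.

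**Working it through.** No sample-size or power figure is involved. The check is a timeline built from the protocol's own times.

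**Inputs**
- Three daily doses, Days 1 to 3 (Section 5.2). Taking them 24 h apart, they fall at 0, 24 and 48 h.
- Reporting closes 24 h after dose 3 (Section 8.1).
- The final visit is 72 h after dose 3 (Figure 4-1, Section 7.1.6).

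**Arithmetic**
- Window closes: 48 + 24 = 72 h from first dose (Day 4).
- Final visit: 48 + 72 = 120 h from first dose (Day 6).
- Gap: 120 − 72 = 48 h.
- Share of the time from first dose to final visit: 48 / 120 = 40%.
- Share of the time after the last dose: 48 / 72 = 67%.

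The 48 h gap does not depend on dose spacing, because both end points are counted from the third dose (72 − 24 = 48). Only the 72 h, 120 h and 40% figures assume 24 h intervals.

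**Safety bloods.** Table 4-1 marks them at screening and at the final visit only. Table 7-1 agrees, with two samples each for chemistry, coagulation and full blood count. Two samples less one at screening leaves one after dosing, on Day 6. The only scheduled post-dose laboratory check is therefore drawn 48 h after the window closes.

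**The sections applied to one case.** Take a serious event that begins on Day 5 in a woman who completes the schedule:
- Section 7.1.6 and Table 4-1: recorded at the Day 6 visit.
- Section 8.1: outside the reporting window.
- Section 8.2, read on its own: reportable immediately.
- Section 8.3: exempt if consistent with the SmPC list.

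Sections 8.1 and 8.2 give opposite answers, and 8.3 may override either.

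**Would a longer window be enough?** Not necessarily. Section 5.3 calls bleeding the most common and severe side effect and refers to the SmPCs for full details. If bleeding is listed in section 4.8 of those documents (an assumption, as they are not at hand), 8.3 could still exempt it on Day 5 or on any other day. Under Section 16, the Day 6 laboratory values would still not reach the trial database.

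**Early termination.** Section 8.4 allows a stop on new safety information and then ends all participant data collection. Read literally, this cancels the Day 6 event record and bloods for any woman who has been dosed but has not yet reached that visit.

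**The case against.** The strongest reply is that nothing need go missing. A reader might infer from 8.1 that late bleeding is lost. The documents do not support that for a woman who completes the schedule, because Section 7.1.6 has her events recorded on Day 6. Section 8.1 limits what is reported, not what is recorded. Section 8.2 can also be read as still requiring a serious Day 5 event to be reported. Both points stand, and they reduce the problem to conflicting reporting rules. They do not remove it, since 8.1 names SAEs expressly and closes the window on them.

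A reader might also infer that every finding from the Day 6 bloods is excluded. Section 8.1 does not say whether the window runs by onset or by detection, so an abnormality found on Day 6 that began earlier could still count. That is one more ambiguity to settle.

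A third tempting reading is that 8.4 contradicts 6.7, under which the investigator should as far as possible "have the subject complete the scheduled discharge assessments". It does not. Section 6.7 deals with the withdrawal of an individual and 8.4 with the end of the whole trial. The 8.4 point therefore stands alone and is narrow: it concerns only women between first dose and Day 6 when the trial stops, in a study of 12.

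Finally, 40% is a share of clock time, not of events or risk, and the endpoints in Sections 4.2 and 4.3 are concentrations and AUCs, which the reporting window does not touch. Both remarks are correct and bear on severity.

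**Conclusion.** The inconsistency is real and follows from the plain text. The 8.1 window ends 48 h before the Day 6 event record, the safety review and the only scheduled post-dose safety bloods, and 8.2 states no end time for serious events. What is at risk is consistent reporting of late events, not their capture in women who complete the schedule.

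The 48 h figure rests only on the two times counted from the third dose; the 40% also assumes doses 24 h apart. How many events would fall in the gap cannot be estimated from the protocol. Whether 8.3 would exempt bleeding in any case depends on SmPC content that is not at hand.

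This should be fixed. It is not a fatal flaw, and the pharmacokinetic results do not depend on it. The 8.4 point is minor and separate.

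**What to change.** In one amendment:

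1. **Section 8.1.** Reconcile it with 7.1.6, Table 4-1, Table 5-3 and 8.2, so that the reporting window covers the event record and safety bloods already scheduled on Day 6. State whether the window runs by onset or by detection.
2. **Section 8.2.** Refer to the same window, or state explicitly which categories are reportable without a time limit.
3. **Section 8.3.** Check whether the exemption for SmPC-listed events is meant to cover bleeding, the named main risk, and whether it applies to serious events. Make clear that exemption from reporting is not exemption from recording.
4. **Section 16.** State how a Day 6 laboratory abnormality enters the adverse-event record when only the date and time of sampling reach the CRF.
5. **Section 8.4 (minor).** Reconcile the stop on data collection with the Day 6 safety assessment of women already dosed. This point does not call for any remaining pharmacokinetic sampling after a stop.

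No new visit or sample is needed. The cost is a few sentences across these sections and possibly a few more adverse-event reports.

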8.2. Procedures for Recording and Reporting Adverse Events

The Medicines for Human Use (Clinical Trials) Regulations 2004 and Amended Regulations 2006 gives the following definitions:

- **Adverse Event (AE):** Any untoward medical occurrence in a participant to whom a medicinal product has been administered, including occurrences which are not necessarily caused by or related to that product.
- **Adverse Reaction (AR):** Any untoward and unintended response in a participant to an investigational medicinal product which is related to any dose administered to that participant.
- **Unexpected Adverse Reaction (UAR):** An adverse reaction the nature and severity of which is not consistent with the information about the medicinal product in question set out in:

The summary of product characteristics (SmPC) for that edoxaban and rivaroxaban.

- **Serious adverse Event (SAE), Serious Adverse Reaction (SAR) or Suspected Unexpected Serious Adverse Reaction (SUSAR):** Any adverse event, adverse reaction or unexpected adverse reaction, respectively, that:
 - results in death;
 - is life-threatening;
 - required hospitalisation or prolongation of existing hospitalisation;
 - results in persistent or significant disability or incapacity;
 - consists of a congenital anomaly or birth defect.
- **Important Medical Events (IME) & Pregnancy:** Events that may not be immediately life-threatening or result in death or hospitalisation but may jeopardise the participant or may require intervention to prevent one of the other outcomes listed in the definition above should also be considered serious. Although not a serious adverse event, any unplanned pregnancy will also be reported via the SAE reporting system.

Reporting Responsibilities

King's College Hospital has delegated the delivery of the Sponsor's responsibility for Pharmacovigilance (as defined in Regulation 5 of the Medicines for Human Use (Clinical Trials) Regulations 2004 to the King's Health Partners Clinical Trials Office (KHP-CTO).

All SAEs, SARs and SUSARs (excepting those specified in this protocol as not requiring reporting) will be reported immediately by the Chief Investigator (and certainly no later than 24hrs) to the KHP-CTO in accordance with the current Pharmacovigilance Policy.

The KHP-CTO will report SUSARs to the regulatory authorities (MHRA, competent authorities of other EEA (European Economic Area) states in which the trial is taking place.

The Chief Investigator will report to the relevant ethics committee. Reporting timelines are as follows:

- SUSARs which are fatal or life-threatening must be reported not later than 7 days after the sponsor is first aware of the reaction. Any additional relevant information must be reported within a further 8 days;
- SUSARs that are not fatal or life-threatening must be reported within 15 days of the sponsor first becoming aware of the reaction.

The Chief Investigator and KHP-CTO (on behalf of the sponsor), will submit a Development Safety Update Report (DSUR) relating to this trial IMP, to the MHRA and REC annually.

8.3. Adverse events that do not require reporting

Adverse events or reactions that are consistent in nature and severity with those listed in Section 4.8 of the relevant SmPC for edoxaban and rivaroxaban do not need to be reported.

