5.3. IMP Risks

As edoxaban and rivaroxaban have been marketed for many years and are widely prescribed, all effects can be reliably predicted in accordance with their Summary of Product Characteristics (SmPC). It is anticipated that the three single doses of edoxaban or rivaroxaban administered should not create emergencies. But in case there is, a member of the research team will be on call 24 hours a day (through mobile number).

Bleeding as a main risk due to healing of a raw area in the uterus (placental site), which could lead to postpartum haemorrhage with serious consequences, will be highlighted to women, before they consent into the trial.

As it has not been demonstrated if edoxaban or rivaroxaban are safe to prescribe during breastfeeding, study volunteers must stop breastfeeding their infants from the first dose until the follow-up period when the study drugs are undetectable in the maternal plasma.

Full details of AEs of edoxaban and rivaroxaban are listed in the respective SmPCs.

The Reference Safety Information (RSI) for all information pertaining to IMP risk for edoxaban and rivaroxaban are set out in the edoxaban and rivaroxaban SmPC.

Based on both the mechanisms described previously, and on clinical experience with edoxaban and rivaroxaban, the known and potential risks to human subjects can be summarised as follows:

It is recognized that the most common and severe side effect of edoxaban and rivaroxaban is bleeding, especially gastrointestinal bleeding, which may be potentially life threatening and require immediate medical attention. To minimize the risk to subjects, individuals with hepatic disease or history of liver problem associated with coagulopathy and clinically relevant bleeding risk, severe kidney disease or dialysis treatment, lesion or condition if considered a significant risk factor for major bleeding (e.g. gastrointestinal ulceration, presence of malignant neoplasms at high risk of bleeding, very high blood pressure or diabetes without medical control, recent brain or spinal injury, recent brain, spinal or ophthalmic surgery, recent intracranial haemorrhage, known or suspected oesophageal varices, arteriovenous malformations, vascular aneurysms or major intraspinal or intracerebral vascular abnormalities) will be excluded from the study.

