All source documents will be retained by the study centre. Photocopies of completed source documents will be provided only if essential (i.e., for regulatory purposes) at the request of the Sponsor.

Safety laboratory data are managed and stored within the KCH system and only the date and time of sampling are recorded on the paper CRF and eCRF.

The original informed consent form will be kept in the ISF with a with a copy filed in the patients notes and a copy given to the patient. Completed source documents will be filed in the appropriate source folder, or a note to indicate where the records can be located. All records will be kept in conformance to applicable national laws and regulations.

All CRF and eCRF entries, corrections and alterations must be made by the Investigator or other authorised study centre staffs. At the end of the study, essential documentation will be archived in accordance with sponsor and local requirements. The retention of study data will be the responsibility of the Chief Investigator.

17. Publication Policy

It is intended that the results of the study will be reported and disseminated at international conferences and in peer-reviewed scientific journals.

18. Insurance / Indemnity

The sponsors - King's College Hospital NHS Foundation Trusts, declares to having insurance cover for the malpractice and/or negligence of their employees and agents. King's College Hospital NHS Foundation Trust indemnity insurance applies.

19. Financial Aspects

Funding to conduct the trial is provided by [name] (CI) research funding.

20. Archiving

At the end of this trial, all trial data will be stored in line with the Medicines for Human Use (Clinical Trials) Amended Regulations 2006 and the 2018 Data Protection Act and archived in line with the Medicines for Human Use (Clinical Trials) Amended Regulations 2006 as defined in the Sponsor Archiving Standard Operating Procedure (SOP).

21. Signatures

7th December 2023

Chief Investigator

[name]

Date

REFERENCES

- Agnelli, G., *et al.* (2013). Oral Apixaban for the Treatment of Acute Venous Thromboembolism. Oral Apixaban for the Treatment of Acute Venous Thromboembolism. *The New England Journal of Medicine*, 369, 799-808.
- Bates, S. M. (2012). VTE, thrombophilia, antithrombotic therapy, and pregnancy: Antithrombotic Therapy and Prevention of Thrombosis, 9th ed: American College of Chest Physicians Evidence-Based Clinical Practice Guidelines. *Chest*, 141 (2 Suppl), e691S-736S.

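### Section 8.3's reporting exemption is not limited to non-serious events, so under Section 8.2 a serious but SmPC-consistent reaction, such as a life-threatening bleed, need not go to the KHP-CTO within 24 hours

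*Protocol*

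**What the plan says.** Four parts of the protocol bear on this.

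- **Section 8.3** covers "Adverse events or reactions that are consistent in nature and severity with those listed in Section 4.8" of the SmPC for each drug, and says that these "do not need to be reported". It does not mention seriousness.
- **Section 8.2** sets the expedited route: "All SAEs, SARs and SUSARs (excepting those specified in this protocol as not requiring reporting) will be reported immediately by the Chief Investigator", no later than 24 hours, to the KHP-CTO, which holds the sponsor's delegated pharmacovigilance responsibility. The same section makes an event serious if it results in death, is life-threatening, requires or prolongs hospitalisation, causes lasting disability, or is a birth defect. It calls a reaction unexpected when its nature and severity do not fit the SmPC.
- **Section 5.3** states that "the most common and severe side effect of edoxaban and rivaroxaban is bleeding". It describes this risk, particularly bleeding from the gut, as one "which may be potentially life threatening and require immediate medical attention". It refers to the SmPCs for the full list of adverse events. It also names bleeding from the healing placental site as a main risk in these women.
- **Section 8.1** ties the safety assessments to the risks in Section 5.3 and says that AEs and SAEs will be reported from the first dose until 24 hours after the third.

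**The concern.** Exempting expected, non-serious events from individual reporting is an ordinary choice in a short study of licensed drugs. Here the exemption is defined by SmPC consistency alone. Because the 24-hour rule excludes whatever the protocol exempts, the exemption passes from routine AEs into serious ones. The events most likely to be both serious and SmPC-consistent are bleeds, which the protocol itself treats as the main hazard.

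What is at stake is prompt sponsor awareness of serious harm in healthy volunteers. Section 8.4 lets the sponsor stop the trial on new safety information, and Section 8.2 has the KHP-CTO co-submit an annual DSUR. Both work better if serious reactions reach that office as they occur. Section 11 rules out a DMC and a TSC, so no independent committee is in place to notice what the expedited route omits.

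**Working it through.** No arithmetic applies and the plan gives no figure to reproduce. The check sets the sections side by side and follows one event through them.

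**Step 1: what the 8.2 exception refers to.** It excludes events that the protocol specifies as not requiring reporting. Section 8.3 is the only section that specifies any, so the two must be read together.

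**Step 2: whether 8.3 excludes serious events from its scope.** Its test is consistency in nature and severity with SmPC section 4.8. Severity (how intense an event is) is not seriousness (the outcome-based criteria in 8.2). A severe listed reaction can pass the 8.3 test and still be serious under 8.2.

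**Step 3: what stays in the 24-hour duty.** Section 8.2 defines unexpected reactions by lack of consistency with the SmPC in nature and severity. Section 8.3 exempts those that are consistent. Among serious reactions the two rules are close to complements: SUSARs stay in, and expected SARs drop out. The word SARs in the 24-hour rule is left almost without content. SAEs unrelated to the drug drop out too if they match a listed event.

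**Step 4: trace a life-threatening gastrointestinal bleed after dosing.**

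| Question | Source | Answer |
|---|---|---|
| Serious? | 8.2, life-threatening criterion | Yes |
| Drug-related? | Assumed for the example | Yes, so a SAR |
| Consistent with the SmPC? | Inferred from 5.3 | Yes, so not a SUSAR |
| Exempt? | 8.3, no seriousness limit | Yes |
| Within the 24-hour duty? | 8.2 exception | No |

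**Step 5: whether another section restores the duty.**

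- Section 8.1 says AEs and SAEs will be reported, but its function is to set a time window. It conflicts with 8.3 and does not say which prevails.
- Section 7.1 and Table 4-1 require adverse events to be recorded at visits. That is collection, not notification of the KHP-CTO.
- Section 10 gives review for harm to the TMG, chaired by the chief investigator, and sets no reporting timeline to the sponsor.
- Sections 12 and 16 give the sponsor access to source data and periodic database reports. These show what was recorded, but carry no 24-hour obligation.

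Nothing found restores the 24-hour duty for an expected serious reaction.

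**The case against.** The strongest reply is that little is actually lost. Adverse events are recorded on Days 1, 2, 3 and 6 with no exclusion for SmPC-listed events. The TMG reviews data for harm. The sponsor receives database reports at agreed intervals and may inspect source documents, including blood test reports. The chief investigator, who would know of any serious bleed, is a joint submitter of the DSUR. All of this stands. It limits the defect to the expedited route, but does not supply that route.

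Several stronger readings are tempting, and the documents do not support them.

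- *Bleeding need not be reported at all.* Too broad. A serious, related bleed that is inconsistent with the SmPC in nature or severity is a SUSAR and stays reportable. Whether placental-site haemorrhage is listed cannot be checked, since the SmPC text is not in the protocol.
- *The expedited route and the database are the only ways a bleeding signal can reach the sponsor.* Sections 10, 12 and 16 show other ways.
- *A count of zero reported bleeds would carry no information, or would exclude only high rates.* Bleeds are still recorded at visits. Bounds on a rate from 6 or 12 women with no events reflect the sample size and would be the same under a perfect Section 8.3. The protocol has no bleeding-rate endpoint.
- *Safety laboratory values are lost because "only the date and time of sampling are recorded on the paper CRF and eCRF" (Section 16).* The values are kept in the hospital system and are open to the sponsor. This is a data-management choice and a separate matter.
- *Every bleed of any severity should be reported.* The contradiction does not require it, and in postpartum women it would raise the question of where ordinary postpartum bleeding ends and an adverse event begins.

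**Conclusion.** The point holds as a drafting defect with a safety consequence. As written, Sections 8.2 and 8.3 together remove serious, SmPC-consistent events from the 24-hour report to the KHP-CTO, in both arms and for all 12 planned participants. Section 8.1 points the other way, and the protocol does not settle the conflict.

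The size cannot be put as a number: it is the loss of one mandatory notification for one class of event, the class containing the main named risk. It should be corrected because it concerns sponsor awareness of serious harm in healthy volunteers, the protocol gives no reason for exempting serious events, and the correction is nearly free.

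The conclusion that 8.3 reaches serious events rests on the wording alone. The bleeding example rests on one further assumption, that SmPC section 4.8 lists bleeding of the relevant kind and severity. This is inferred from Section 5.3.

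**What to change.** Reconcile Sections 8.1 to 8.3 in one amendment:

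1. In Section 8.3, limit the exemption to non-serious events.
2. In Section 8.2, state that all SAEs and SARs, including serious bleeding, go to the KHP-CTO within 24 hours whether or not the event is listed in the SmPC, and make the exception clause agree with this.
3. State that expectedness against the SmPC decides only whether a serious reaction is classed as a SUSAR.
4. In Section 8.1, refer to Section 8.3 so that the general statement on reporting and the non-serious exemption no longer conflict.

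The cost is the amendment wording and slightly more SAE paperwork. No change is needed to the design, sample size, visits or sampling.
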